### **Windows for multiple assessments**

In order to summarize hematological response collected over time, the assessments will be time slotted. The following general rule will be applied in creating the assessment windows: If more than one assessment is done within the same time window, the assessment performed closest to the target date will be used. If 2 assessments within a time window are equidistant from the target date, then the earliest of the 2 assessments will be used. Notice that, if there are scheduled and unscheduled assessments in the same time window, the scheduled assessment will be used. Data from all assessments (scheduled and unscheduled), including multiple assessments, will be listed.

**Table 2-1 Time windows for hematological response**

Assessment	Target day of assessment	Time Interval
Baseline	On or before Study Day 1	≤ Day 1
Week 13	Week 13 ± 3 days	Study Day 77 – 105 (i.e. 11 to 15 weeks)
Week 26	Week 26 ± 3 days	Study Day 168 – 196 (i.e. 24 to 28 weeks)
Week 52	Week 52 ± 7 days	Study Day 336 – 392 (i.e. 48 to 56 weeks)
Year 2	Week 104 ± 30 days	Study Day 672 – 784 (i.e. 96 to 112 weeks)
Year 3	Week 156 ± 30 days	Study Day 1036 – 1148 (i.e. 148 to 164 weeks)

### **Last contact date**

The last contact date will be derived for patients not known to have died at the analysis cut-off date using the latest complete date among the following:

- All assessment dates (e.g. vital signs assessment, collection of blood sample for laboratory testing, ECG, bone marrow biopsy, etc.)
- Medication dates including study medication and concomitant medications.
- Adverse events dates
- Survival follow-up dates

The last contact date is defined as the latest complete date from the above list on or before the data cut-off date. The cut-off date will not be used for last contact date, unless the patient was seen or contacted on that date. No date post cut-off date will be used. Completely imputed dates (e.g. the analysis cut-off date programmatically imputed to replace the missing end date

of a dose administration record) will not be used to derive the last contact date. Partial date imputation is allowed for event (death)/censoring if coming from 'Survival' eCRF.

The last contact date will be used for censoring of patients in the analysis of overall survival.

## **2.2 Analysis sets**

### **Full Analysis Set**

The Full Analysis Set (FAS) comprises all subjects to whom study treatment has been assigned and who received at least one dose of study treatment.

### **Safety Set**

The Safety Set includes all subjects who received at least one dose of study treatment. All safety analyses will be done using the Safety Set.

### **Pharmacokinetic analysis set (PAS)**

The Pharmacokinetic analysis set (PAS) includes all subjects who received at least one dose of eltrombopag and provide at least one evaluable PK sample. However, only evaluable PK samples will be included in the PK analysis. A concentration will be flagged as NOT evaluable programmatically if any of the following conditions is satisfied:

- The dose received is not the protocol-planned dose in any of the 7 consecutive days prior to the current dose.
- Vomiting occurs within 4 hours of the last dose (pre-dose trough sample).
- Vomiting occurs within 4 hours of the current dose (post-dose samples).

Only PK concentrations/parameters which are not flagged for exclusion programmatically will be used for summaries or statistical analysis. Any concentration listings will include all concentration values, with flags indicating those excluded from analyses.

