recommended when eltrombopag is co-administered with CsA. Platelet count should be closely monitored when eltrombopag is co-administered with CsA and eltrombopag dose may need to be adjusted based on these platelet counts.

Co-administration of a single dose of eltrombopag 75 mg with a polyvalent cation containing antacid (1.524 mg aluminum hydroxide, 1.425 mg magnesium carbonate, and sodium alginate) decreased the plasma eltrombopag AUCinf and Cmax by 70% and 70%, respectively. It is therefore recommended to take eltrombopag at least 2 hours before or 4 hours after other medications (e.g., antacids), calcium-rich foods (e.g., dairy products and calcium-fortified juices), or supplements containing polyvalent cations such as iron, calcium, aluminum, magnesium, selenium, and zinc. Foods low in calcium (defined as <50 mg calcium per serving) including fruit, lean ham, beef and unfortified (no added calcium, magnesium, iron) fruit juice, unfortified soy milk, and unfortified grain did not significantly impact plasma eltrombopag exposure, regardless of calorie and fat content. Eltrombopag is recommended to take at least one hour before or two hours after food containing little (< 50 mg) (or preferably no) calcium.

Asian ethnicity (such as Chinese, Japanese, Taiwanese, Korean, or Thai) has consistently been associated with lower eltrombopag apparent clearance (CL/F) of approximatively 30 to 37%, translating into higher plasma eltrombopag exposure across different patient populations. Asian patients had approximately 50% to 90% higher plasma eltrombopag exposures than non-Asian patients. SAA patients of East-Asian ethnicity need to decrease the initial dose by 50% relative to Caucasian, according to eltrombopag Label approved by US food and drug administration (FDA) and the european medicines agency (EMA). The initial doses for Chinese ≥ 12 year-old ITP participants (approved by CDE) and Japanese adult SAA participants (approved by pharmaceuticals and medical devices agency (PMDA)), were identical with those for East Asian participants in US and EMA label.

Additional information can be found in the Investigator's Brochure and summary of product characteristics in eltrombopag package insert.

2 Objectives and endpoints

For the definition of response, partial response (PR), CR, transfusion independence, and relapse, refer to [Section 8.3](#).

Table 2-1 Objectives and related endpoints

[figure not shown]
Objective(s)	Endpoint(s)

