Participants requiring routine (e.g. daily) acid suppression should be encouraged to take H2 antagonists or proton pump inhibitors. Participants requiring occasional acid suppression may take liquid or chewable antacids provided eltrombopag is taken at least two hours before or four hours after any consumption of polyvalent cation containing antacids.

Food Interaction

To minimize impact of food in eltrombopag absorption, eltrombopag must be taken at least one hour before or two hours after food containing little (<50 mg) or preferably no calcium. Administration of a single 50 mg-dose of eltrombopag with a standard high-calorie, high-fat breakfast that included dairy products reduced plasma eltrombopag AUC_{inf} by 59% (90% CI: 54%, 64%) and C_{max} by 65% (90% CI: 59%, 70%). Foods low in calcium (defined as <50 mg calcium per serving) including fruit, lean ham, beef and unfortified (no added calcium, magnesium, iron) fruit juice, unfortified soy milk, and unfortified grain did not significantly impact plasma eltrombopag exposure, regardless of calorie and fat content.

Drugs affecting coagulation/bleeding

The following drugs have a possibility that affects the assessment of bleeding. And in the event their use is clinically indicated and cannot be avoided under the discretion of investigator, those drugs will be permitted, but the participant(s) will be excluded from bleeding analyses during the time period the participant was exposed to the medication.

- Drugs that affect platelet function (including but not limited to, aspirin, clopidogrel and/or non-steroidal anti-inflammatory drugs [NSAIDs])
- Anticoagulant (warfarin, heparin, etc.)

R-ATG

Thymoglobulin can stimulate the production of antibodies that cross-react with other rabbit immune globulins, therefore concomitant use of other rabbit immune globulins should be avoided. If they cannot be avoided, cautions should be used during concomitant administration with r-ATG.

CsA

The concomitant use of CsA with the following requires caution:

- Potassium or potassium supplements, potassium-sparing diuretics, angiotensin converting enzyme inhibitors, angiotensin II receptor antagonists which may result in significant increases in serum potassium;

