Variable	15	24 h (± 1 h) ^d /0 h (Pre-dose) ^{a,d}	2+ ^e /103+ ^f	7+ ^g
Unscheduled	Unscheduled	Unscheduled ^h	NA	1001+ ^h

Week from the first dose	Day from new dose started	Scheduled time point	Dose reference ID	Sample number
* ^a : these samples are only collected for 1) the first 12 Chinese adult participants who signed the informed consent to participate in the PK study, receiving 75 mg/day, 2) all Japanese pediatric participants at initial dose. a: Collect PK sample immediately before drug administration (not more than 1 h prior to dosing); b: Dose administration record after PK sampling ; c: Dose administration record before PK sampling; d: Collect pre-dose PK blood sample on the 15 th day after each new dose has started (dose reduction criteria: 75, 50 and 25 mg/day for the participants \geq 12 years old; 37.5, 25 and 12.5 mg/day for participants \geq 6 and < 12 years old); e: Dose reference ID will be sequentially numbered 2, 3 for the last dose prior to pre-dose PK sampling after each new dose started, f: Dose reference ID will be sequentially numbered 103,104 for dose after pre-dose PK sampling; g: Sample number will be sequentially numbered 7, 8 when the PK blood sample is taken at pre-dose on Day 15 after each new dose started; h: Unscheduled PK blood samples may be collected at any time for measurement of plasma drug concentrations if clinically indicated or at the Investigator's discretion and will be uniquely, sequentially numbered as 1001, 1002, etc.				

In case of DILI, an unscheduled eltrombopag PK sample should be collected.

On the days of PK sample collection, the participant will be advised to take investigational drug after the pre-dose blood sample is taken.

The sample collection must be captured on appropriate eCRF and requisition form(s). The actual date and time of each PK sample collection will be integrated in the eCRF via data transfer.

Additionally, for PK analysis purposes, the following information about the most recent dose prior to the visit (or DILI) will be recorded in the eCRF:

- Date and time of dosing.
- Whether or not eltrombopag was taken at empty stomach (1 hour before or 2 hours after a meal) or at least 2 hours before or 4 hours after polyvalent cations and dairy products.
- Whether or not the participant vomited after receiving eltrombopag within 4 hours of dosing.

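### The evaluable-PK rule uses the recorded vomiting answer but not the fasting and cation/dairy answer collected beside it, so affected troughs enter the PK summaries unmarked

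*SAP*

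**What the plan says.** Protocol 12.1 leaves the definition of an evaluable PK sample to the SAP. The primary-analysis SAP gives it in 2.2 under the pharmacokinetic analysis set: "A concentration will be flagged as NOT evaluable programmatically if any of the following conditions is satisfied". Three conditions follow. The first is "The dose received is not the protocol-planned dose in any of the 7 consecutive days prior to the current dose". The other two concern vomiting within 4 hours, of the last dose for troughs and of the current dose for post-dose samples. The consequence is then stated: "Only PK concentrations/parameters which are not flagged for exclusion programmatically will be used for summaries or statistical analysis".

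Protocol 8.5.1.1 lists what the eCRF must hold about the most recent dose before the visit, expressly for PK analysis. There are three items: date and time of dosing, vomiting within 4 hours, and a food and cation item that begins "Whether or not eltrombopag was taken at empty stomach (1 hour before or 2 hours after a meal" and continues, joined by 'or', with the separation from polyvalent cations and dairy.

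SAP 2.9 adds a rule for samples taken outside their time window and rules for values below the quantification limit. It does not mention the food and cation item, and neither does Protocol 12.5.3. The final-analysis SAP declares PK not applicable, so the primary-analysis rule is the only one.

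**The concern.** Two answers about the same dose are collected side by side for the same purpose. One decides whether a sample counts; the other has no analytic effect. The protocol itself treats the unused one as important to exposure. Section 1.3 reports that a cation-containing antacid "decreased the plasma eltrombopag AUCinf and Cmax by 70% and 70%, respectively". Section 6.2.1.1 reports that a single dose taken "with a standard high-calorie, high-fat breakfast that included dairy products" lost 59% of AUCinf and 65% of Cmax.

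Eltrombopag PK in East-Asian patients is a secondary objective of a study that the SAP describes as bridging to support registration. The groups are small: 12 Chinese adults and all Japanese paediatric participants (3 planned) give full profiles, and everyone else gives one trough per dose level. Samples after a poorly separated dose pull Ctrough down and widen its CV, and the reader of the tables would have no sign of it.

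**Working it through.** **Text check.** The table sets the items recorded for PK analysis against their use.

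| Recorded (Protocol 8.5.1.1) | Used in SAP 2.2 or 2.9? |
|---|---|
| Date and time of dosing | 2.9 sets a timing rule for off-window samples |
| Vomiting within 4 h | Yes, two conditions in 2.2 |
| Fasting, or cation/dairy separation | No |

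**Inputs.** Half-life 21–32 h and Tmax 2–6 h (Protocol 1.3); once-daily dosing, so τ = 24 h (6.7.2); loss from one affected dose r = 0.59 (dairy breakfast, 6.2.1.1) or 0.70 (antacid, 1.3). Both losses are single-dose AUCinf results of other studies and cannot be re-derived here. The documents give no steady-state figure to reproduce.

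**Assumption.** Linear one-compartment kinetics with superposition.

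**Step 1: share of the steady-state trough supplied by the last dose.** With k = ln 2 / t½, the share is 1 − exp(−kτ).
- t½ = 21 h: 1 − 0.453 = 0.547
- t½ = 32 h: 1 − 0.595 = 0.405

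**Step 2: trough loss after one affected dose**, L = r × share.

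| | r = 0.59 | r = 0.70 |
|---|---|---|
| t½ = 21 h | 32.3% | 38.3% |
| t½ = 32 h | 23.9% | 28.4% |

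First-order absorption with Tmax of 2 h or 6 h leaves these trough figures unchanged.

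**Step 3: the ceiling.** If m consecutive doses are affected, L = r × (1 − exp(−mkτ)). After 7 days, 0.4% (21 h) or 2.6% (32 h) of earlier drug remains. The loss is then between 0.59 × 0.974 = 57% and 0.70 × 0.996 = 70%. The full 59–70% thus needs repeated lapses, and an item about the last dose alone cannot show that pattern.

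**Step 4: full profiles.** If the dose given on the PK day were itself affected, AUCtau would fall by 22.5–37.8%. CLss/F would then rise by 1/(1 − 0.225) − 1 = 29% to 1/(1 − 0.378) − 1 = 61%. That dose is taken in clinic when staff instruct (6.1.1.1, 6.7.2), so this is the less likely route. If only the previous day's home dose is affected, the AUCtau loss is approximately r × share × exp(−kτ), taking absorption as rapid. This runs from 0.59 × 0.405 × 0.595 = 14% to 0.70 × 0.547 × 0.453 = 17%.

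**Step 5: effect of one affected participant on a geometric mean**, 1 − (1 − L)^(1/n).
- n = 12: 1 − 0.76^(1/12) = 2.3% to 1 − 0.62^(1/12) = 3.9%
- n = 3: 1 − 0.76^(1/3) = 8.7% to 1 − 0.62^(1/3) = 14.7%; the lowest AUCtau loss gives 1 − 0.775^(1/3) = 8.1%
- n = 36, if all initial-dose troughs were pooled: 0.8% to 1.3%

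Three affected participants among 12 would give 6.6–11.3%. The number affected is an assumption throughout, because the documents do not give it.

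**The case against.** The case for leaving the rule alone has real substance.

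- Collecting the item for PK analysis does not commit the sponsor to excluding anything. It could serve interpretation, or the exposure-response work that SAP 2.10 leaves to a separate report. This stands, and it argues against mandatory exclusion. It does not explain why the planned summaries ignore the answer.
- Separation is mandated in Protocol 6.2.1.1 and 6.7.2, and PK-day doses are taken in clinic. This stands for post-dose samples. It does not protect a pre-dose trough after a home dose, and for participants outside the intensive group that trough is the only scheduled sample at each dose level.
- Protocol 6.2.1.1 says low-calcium food has no significant effect on exposure, so a negative answer may be harmless. The 'or' in the item also lets a positive answer hide one failure. Both points stand. The item is an imperfect marker, and dropping every negative answer could discard valid data from very small groups.
- The PK summaries are descriptive, the 12 profiles were chosen on feasibility, and the frequency is unknown. This limits the weight of the point but does not remove it.

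Two stronger readings are tempting. A reader might infer that retained samples are low by 59–70%. Those are single-dose figures, and the one recorded dose implies 24–38% on a steady-state trough. A reader might also infer that the vomiting rule removes smaller errors than those it leaves in. The documents give no exposure figure for vomiting, so that comparison has no basis.

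**Conclusion.** The omission is confirmed by the text: a recorded failure of fasting or cation/dairy separation has no effect on any planned PK summary. The consequence is modest for groups of 12 and noticeable for a group of 3, at the sizes worked out above, and it falls mainly on Ctrough. These sizes rest on linear one-compartment kinetics, on carrying single-dose losses over to steady state, and on one affected participant. The primary endpoint and the other efficacy analyses are unaffected. This is a cheap improvement to a secondary objective, not a flaw that would invalidate the PK results.

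**What to change.** In primary-analysis SAP 2.2 and 2.9:

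1. Flag every concentration whose governing dose has a negative answer on the food and cation item. The governing dose is the last dose for pre-dose samples and the current dose for post-dose samples.
2. Report the number of flagged samples and participants by dose level and age group.
3. Present the Ctrough and PK-parameter summaries both with and without the flagged values, and keep all values in the listings with the flag shown. Do not make exclusion automatic.
4. State in a footnote that the item joins two conditions with 'or', so a positive answer may hide one failure and a negative one may reflect low-calcium food. If source data allow the two parts to be separated, report them separately.

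The cost is one flag from an existing eCRF field and one extra set of descriptive summaries, with slightly fewer samples in the restricted version.

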### **Withdrawal of Informed Consent**

Any data collected in the clinical database after a subject withdraws informed consent from all further participation in the trial, will not be included in the analysis. The date on which a patient withdraws full consent is recorded in the eCRF.

#### **2.2.1 Subgroup of interest**

The following subgroups will be considered for outputs. Details of the use of these subgroups will be found in the sections for the relevant endpoints.

### **Efficacy**

The primary efficacy endpoint will be summarized by the following subgroups:

- Age : (< 18 years) vs. (18-64 years) vs. ( $\geq$  65 years)

The primary efficacy endpoint will be further summarized by subgroups of paediatric patients defined as (6-11 years) and (12-17 years).

No formal statistical test of hypotheses will be performed for the subgroups, only point estimate of the treatment effect and 95% confidence intervals will be provided (see [Sections 2.5.4](#) for further analysis details).

## **Safety**

Key safety analyses (all AEs, AEs with suspected relationship to study treatment and/or eltrombopag, SAEs, SAEs with suspected relationship to study treatment and/or eltrombopag and AESIs) will be repeated in the following subgroups:

- Age : (< 18 years) vs. (18-64 years) vs. ( $\geq$  65 years)

The key safety endpoint will be further summarized by subgroups of paediatric patients defined as (6-11 years) and (12-17 years). The objective for carrying out these subgroup analyses is to identify potential safety issues that may be limited to a subgroup of patients, or safety issues that are more commonly observed in a subgroup of patients.

## **Pharmacokinetics**

PK parameters summaries will be repeated for the following subgroups:

- Age : (< 18 years) vs. (18-64 years) vs. ( $\geq$  65 years)
- Gender : Male vs. Female

The PK parameters will be further summarized by subgroups of paediatric patients defined as (6-11 years) and (12-17 years).

The objective for carrying out these subgroup analyses is to identify potential differences in PK parameters between subgroups of patients.

## **China Mainland/Japan specific subgroup analysis**

China Mainland subgroup analysis will be displayed in one separate column as overall population in each table.

Key efficacy, safety, and pharmacokinetics outputs, including demographic and baseline characteristics will be repeated for both the subjects enrolled in sites from Japan and whose age  $< 18$  years. Both subgroup analysis will support Japan submission.

## **2.3 Patient disposition, demographics and other baseline characteristics**

The Full Analysis Set (FAS) will be used for all baseline and demographic summaries and listings unless otherwise specified. No inferential statistics will be provided.

### **Basic demographic and background data**

All demographic and baseline disease characteristics data will be summarized and listed. Categorical data (e.g. gender, age groups: <18, further broken down as 6-11 and 12-17, 18-64,

≥ 65 years, race, ECOG or Lansky performance status) will be summarized by frequency counts and percentages; the number and percentage of patients with missing data will be provided when appropriate. Continuous data (e.g. age, weight, height) will be summarized by descriptive statistics (N, mean, median, standard deviation, minimum and maximum).

Disease history and characteristics at screening including time since initial diagnosis to first dose, platelet count, haemoglobin, absolute neutrophils count (ANC) and absolute reticulocytes count (ARC) will be summarized by statistics for quantitative variables. RBC and Platelet Transfusion (Independence and Dependence) at baseline will be summarized by frequency counts and percentages. Severity of aplastic anemia and result of cytogenetic analysis as defined below, will be summarized by frequency counts and percentages.

- Severity of aplastic anemia (severe vs. very severe where the latter is defined as absolute neutrophil count < 200/ $\mu$ L).

## **Medical history**

Medical history and baseline symptoms (current medical conditions) will be summarized and listed. The summaries will be presented by primary system organ class (SOC) and preferred term (PT). Medical history and current medical conditions will be coded using the Medical Dictionary for Regulatory Activities (MedDRA) terminology. The MedDRA version used for reporting will be specified in the CSR and as a footnote in the applicable tables/listings.

## **Other**

All data collected at baseline will be listed.

### **2.3.1 Patient disposition**

Enrollment by country and center will be summarized for all screened patients. The number (%) of treated patients included in the FAS will be presented. The number (%) of screened and not-treated patients and the reasons for screening failure will also be displayed. The number (%) of patients in the FAS who are still on treatment, who discontinued the study phases and the reason for discontinuation will be presented.

The following summaries will be provided (with % based on the total number of FAS patients):

- Number (%) of patients who are still on-treatment;
- Number (%) of patients who completed core treatment phase;
- Number (%) of patients who discontinued from core treatment phase ;
- Primary reason for the premature discontinuation from core treatment phase;
- Number (%) of patients who have entered extension treatment phase;
- Number (%) of patients who completed the extension treatment phase;
- Number (%) of patients who discontinued from extension treatment phase;
- Primary reason for the premature discontinuation from extension treatment phase;
- Number (%) of patients who have entered the long term follow-up phase;
- Number (%) of patients who completed the long term follow-up phase;
- Number (%) of patients who discontinued from long term follow-up phase;

